3.1 STUDY POPULATION

Premature infants < 17 days of age and their mothers

3.1.1 Inclusion Criteria

- 1. Infants with gestational age 25 0/7 29 6/7 at birth
- 2. Birth weight ≥ 500 grams
- 3. Admitted within the 1st week of life
- 4. < 17 days of age at time of enrollment

3.1.2 Exclusion Criteria

- 1. Infants admitted after the 1st week of life
- 2. Major congenital anomalies
- 3. Structural genitourinary abnormality
- Renal dysfunction (serum creatinine > 1.0 mg/dl or an increase of ≥ 0.3 mg/dl between the 2 most recent consecutive measurements) immediately prior to the initiation of study procedures.
- 5. Diuretic use less than 48 hours prior to initiation of study procedures
- 6. Infant with an ostomy (infants receiving an ostomy after study entry will be withdrawn)
- 7. Infant with a diagnosis or suspicion of diabetes insipidus

This study will also include the mother of the infant to collect information from the mother's chart.

3.2 DETAILED STUDY PROCEDURES

- All study events described below have a ±2 day range for execution.
- Doubly labeled water procedure will occur from corrected week 32 to corrected week 32 + 6 days
- Date of birth is considered day 0
- See Appendix for table of events

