Physiologic Approach to Sodium Supplementation in Premature Infants (Salt to Grow)

Study Investigator: [name] Collaborators: [name] Medical College of Wisconsin [name] **Baylor College of Medicine** Version Date: October 17, 2022 Thrasher Research Fund Funding: Award Number 14651 ClinicalTrials.gov NCT: 03889197 IRB Number: 1902815407

CONTENTS:

Section 1. Abstract - 3

Section 2. Statement of Problem - 5

Section 3. Methods - 11

Section 4. Adverse Events and Reporting - 17

Section 5. Safety, Data Management, and Analysis Plan - 19

Section 5. References – 22

Section 6. Appendix - 25

SECTION 1. ABSTRACT

Study Hypothesis/Question

Aim: To determine the effects on somatic growth (weight, length, head circumference) of adherence to a clinical practice algorithm utilizing urinary sodium concentration to guide sodium supplementation as compared to current treatment practices in preterm infants.

Study Design Type

Prospective, pragmatic, randomized trial comparing a clinical practice algorithm to current treatment practices.

Sample Size

N = 90 patients (Infant and mother dyads)

Eligibility Criteria

Inclusion:

- 1. Infants with gestational age 25 0/7 29 6/7 at birth
- 2. Birth weight ≥ 500 grams
- 3. Admitted within the 1st week of life
- 4. < 17 days of age at time of enrollment

Exclusion:

- 1. Infants admitted after the 1st week of life
- 2. Major congenital anomalies
- 3. Structural genitourinary abnormality
- Renal dysfunction (serum creatinine > 1.0 mg/dl or an increase of ≥ 0.3 mg/dl between the 2 most recent consecutive measurements) immediately prior to the initiation of study procedures.
- 5. Diuretic use less than 48 hours prior to initiation of study procedures
- 6. Infant with an ostomy (infants receiving an ostomy after study entry will be withdrawn)
- 7. Infant with a diagnosis or suspicion of diabetes insipidus

This study will also include the mother of the infant to collect information from the mother's chart.

Study Intervention/Methods

Beginning on the 14-16th postnatal day and continuing until 36 weeks postmenstrual age, infants randomized to the algorithm will have a spot urine sodium concentration determined every two weeks with additional sodium supplementation provided according to the algorithm.

Assessment of total body water and energy expenditure will be made at 32 weeks corrected age by the doubly-labeled water method on all enrolled patients.

Primary Outcome

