Twenty-three (58%) of infants had initial (2-week measurement) urine Na concentration warranting supplementation; while another 7 of infants had low urine sodium concentration] at 4 wk, warranting supplementation. Thus, 75% of infants cared for using this algorithm received sodium supplementation above that in their normal diet. Daily Na intake was similar at 2 wk in both cohorts, but significantly greater (p <0.05) at 4, 6 and 8 wk in the 2016 vs. 2014–2015 cohort (Table). Weight gain, determined as change in weight Z-score between 2 and 8 wk of age, was significantly greater in 2016 vs. 2014–2015 cohort (0.32 ± 0.06 vs. -0.01 ± 0.08, p<0.01). Caloric, protein and total fluid intakes as well as daily urine output were similar between cohorts at the measured time points of 2, 4, 6 and 8 weeks of age (Table). Use of the algorithm did not negatively impact respiratory morbidity at either 28 days of postnatal age (or at 36 weeks postmenstrual age (2014-2015 cohort: 60% receiving supplemental oxygen; 2016 cohort: 48% receiving supplemental oxygen). Since initiating use of this algorithm, no infant has required sodium supplementation to be discontinued due to hypernatremia (serum [Na] >144 mEq/L). These data suggest the physiologically based algorithm to individualize identification of need for sodium supplementation in the preterm infant resulted in increased sodium intake and growth in this population. Given the potential benefits of this approach on growth and ultimately neurodevelopmental outcome, a randomized controlled

Table. Sodium, caloric and protein intakes at increasing postmenstrual ages

trial to evaluate the efficacy of this approach is needed.

Postmenstrual Age							
2 wk	4 wk	6 wk	8 wk				
3.5 ± 0.2	3.8 ± 0.2	3.8 ± 0.2	3.2 ± 0.1				
3.7 ± 0.3	5.3 ± 0.2*	5.7 ± 0.3*	4.4 ±0.2*				
112 ± 3	119 ± 3	119 ± 3	125 ± 4				
115 ± 3	116 ± 2	121 ± 2	120 ± 2				
4.1 ± 0.1	3.9 ± 0.1	4.2 ± 0.1	4.0 ± 0.1				
4.2 ± 0.1	4.0 ± 0.1	4.0 ± 0.1	3.9 ± 0.1				
140 ± 2	147 ± 1	146 ± 1	148 ± 3				
139 ± 2	146 ± 2	147 ± 1	149 ± 2				
73 ± 3	83 ± 2	86 ± 3	93 ± 2				
75 ± 2	85 ± 2	85 ± 3	95 ± 3				

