5.2.3 Sample size and power estimates

Sample size and power calculations for this study are based upon the primary outcome of differences in weight gain between the two groups of infants. Using data from our recently completed analysis, in which infants 26 – 29 6/7 weeks gestation treated according to the algorithm were compared with historical controls, and based upon identifying a difference in weight Z-score of 0.25 at 36 weeks postmenstrual age, using a SD of 0.4 with an alpha = 0.05 and power of 0.8, we calculate we will need a total sample size of 82 patients (41 per group). With regards to the secondary outcome of EE, and based upon published data of EE estimated in preterm infants using the DLW method, a sample size of 41 patients per group will allow us to detect a 6% difference in EE, assuming an alpha = 0.05 and a power of 0.80. With regards to TBW, and based upon data from these same investigators who report a mean TBW of 80.8% body weight, with SD of 3.1%, this sample size will allow us to detect a difference in TBW of 2.0% between groups, assuming an alpha = 0.05 and a power of 0.80. To acknowledge for study drop out, we will plan to enroll up to 90 patients (plus 90 mothers for chart review).

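### The doubly-labeled-water window is not tied to the start of the algorithm, so infants born late in week 29 can be measured before, or only days after, their first urine-sodium decision

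*Combined protocol and SAP*

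**What the plan says.** Section 3.2 sets the measurement of energy expenditure (EE) and total body water (TBW) by postmenstrual age alone: "Doubly labeled water procedure will occur from corrected week 32 to corrected week 32 + 6 days". The same list adds "Date of birth is considered day 0" and "All study events described below have a ±2 day range for execution". The abstract (Study Intervention/Methods) dates the first urine-sodium check: "Beginning on the 14-16th postnatal day and continuing until 36 weeks postmenstrual age". Section 3.1.1 admits "Infants with gestational age 25 0/7 29 6/7 at birth" and allows enrolment while the infant is "< 17 days of age at time of enrollment", that is, through day 16.

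No sentence makes the tracer wait for the first urine-sodium decision or for any minimum time on the algorithm. Section 3.2.6 presents the varying interval as intended. It gives 3 weeks for 29-week births and 7 weeks for 25-week births, and describes both as time after supplementation first begins.

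Section 5.2.3 derives 41 per group from weight Z-score and then states that "a sample size of 41 patients per group will allow us to detect a 6% difference in EE", with 2.0% for TBW. Hypothesis 2 expects lower EE and no TBW difference in the algorithm arm.

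**The concern.** Aim 2 asks what the algorithm does to EE and TBW. An infant measured before the algorithm has acted can show none of its effect, but still counts in the arm mean and pulls the difference toward zero. For EE, where a decrease is predicted, that costs power. For TBW, where no difference is predicted, it makes the predicted result easier to obtain and less informative.

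The upper end of the gestational-age range is where this can happen. The window opens at a fixed postmenstrual age, whereas the algorithm starts at a fixed postnatal age, and for births late in week 29 the two nearly coincide.

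**Working it through.** **Timing.** Inputs: window 32 0/7 to 32 6/7 (224 to 230 days), birth as day 0, first decision on day 14-16. Window opening in postnatal days = 224 − gestational age in days; closing = 230 − gestational age in days.

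| Born at | Days | Window (postnatal day) | Days from a day-14 decision | From day 16 | From day 18 (±2 added) |
|---|---|---|---|---|---|
| 29 0/7 | 203 | 21-27 | 7 to 13 | 5 to 11 | 3 to 9 |
| 29 3/7 | 206 | 18-24 | 4 to 10 | 2 to 8 | 0 to 6 |
| 29 4/7 | 207 | 17-23 | 3 to 9 | 1 to 7 | −1 to 5 |
| 29 5/7 | 208 | 16-22 | 2 to 8 | 0 to 6 | −2 to 4 |
| 29 6/7 | 209 | 15-21 | 1 to 7 | −1 to 5 | −3 to 3 |

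Negative values mean the tracer precedes the decision. On the printed days 14-16 this is possible only at 29 6/7, with 29 5/7 on the same day at worst. With ±2 days added to the decision, it is possible for 29 4/7 to 29 6/7. Whether ±2 days also widens the tracer window (to day 13 at 29 6/7) is unclear, and I have not used it.

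**Section 3.2.6.** At 32 0/7 an infant born at 29 0/7 is 21 days old and one born at 25 0/7 is 49 days old. The stated 3 and 7 weeks are therefore postnatal ages. Counted from day 14, the intervals at opening are 7 days and 35 days.

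**What each measure captures.** TBW comes from the zero-time intercept of deuterium enrichment, so it reflects status at dosing and can precede any decision. EE comes from elimination over about 5 days. An infant dosed on day 15 is sampled to about day 20, so at least the last part of the EE period follows a decision on day 16 or even day 18.

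**The plan's own figures** (two-sided alpha 0.05, power 0.80; 1.960 + 0.842 = 2.802):
- Weight: 2 × 2.802² × (0.4/0.25)² = 40.2, rounded up to 41 per group. This matches.
- TBW: 2.802 × 3.1 × √(2/41) = 1.92 points (1.94 by t-test), consistent with the printed 2.0.
- EE: no SD is given. A 6% difference at 80% power implies a coefficient of variation of 6 / (2.802 × √(2/41)) = 9.7%.

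**Attenuation of EE.** Let f be the share of infants with no effect at measurement, and suppose a 6% effect in all others. The arm-average effect is 6 × (1 − f), and power = Φ[6(1 − f) / (9.7 × √(2/41)) − 1.96]. The values of f assume births spread uniformly over the 35 eligible gestational days.

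| Infants with no effect | f | Average effect | Power |
|---|---|---|---|
| None | 0 | 6.00% | 80% |
| 29 6/7 only | 1/35 | 5.83% | 78% |
| 29 4/7 to 29 6/7 | 3/35 | 5.49% | 73% |
| All of week 29 | 7/35 | 4.80% | 61% |

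If all 29-week infants showed half the effect, the average would be 5.40% and power 71%.

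**The case against.** Section 3.2.6 discloses the varying interval and gives a reason for it: measuring at one postmenstrual age shows change with time since supplementation began. EE and TBW are secondary outcomes. Dosing before the decision is permitted, not inevitable, and on the printed days it concerns one gestational day. Randomisation is stratified by gestational age, so short exposure should be similarly frequent in both arms. Moving 29-week infants late in the window also makes postmenstrual age at measurement depend somewhat on gestational age at birth.

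Most of this stands, and it limits the point to attenuation in a small group. It does not remove the gap. The disclosed intervals are ones that no 29-week infant can reach, even on the last permitted day, and 5.2.2 specifies no analysis by exposure time.

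Some stronger readings are tempting, but the documents do not support them:
- A reader might infer that 5.2.3 assumes 41 fully exposed infants per arm. It makes no exposure assumption: 41 comes from weight Z-score, and under intention-to-treat the 6% and 2.0% are differences between whole arms.
- A reader might infer that, among infants born at 28 0/7 or later, only those low at the 2-week check can be supplemented before measurement. The serum-sodium rule in 3.2.4 applies regardless of urine sodium, and day 28 falls inside the window of every 28-week infant (days 28-34 at 28 0/7, 22-28 at 28 6/7).
- A reader might add the pilot's partial uptake ("Twenty-three (58%) of infants had initial (2-week measurement) urine Na concentration warranting supplementation") as further dilution. Not every infant qualifies for sodium in any comparison of an algorithm with current practice, and the tracer window does not cause that.

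**Conclusion.** The timing gap is real and follows from the protocol's own dates. It is permitted for births at 29 6/7 on the printed days, and for 29 4/7 to 29 6/7 if the ±2 days applies to the urine check. All 29-week infants have at most 7 days on the algorithm at opening and 13 at closing, counted from day 14.

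The likely cost is modest: EE power of about 73-78% instead of 80%. This assumes a uniform gestational-age distribution, early dosing in the affected infants, no effect in them and a 6% effect in the rest. The 61% figure needs zero effect in every 29-week infant and is only an outer bound. It would be wrong to conclude that EE can be measured wholly before the decision, since sampling runs past it; only TBW can be. It would also be wrong to infer bias between arms. This is a cheap improvement worth making, not a flaw that threatens the trial.

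**What to change.** 1. In 3.2 and 3.2.6, keep the 32 0/7 to 32 6/7 window, but require that the tracer follow completion of the 2-week decision point. Controls have no study urine check, so apply the same postnatal-day minimum to them. This is always feasible: even with a decision on day 18, the window of a 29 6/7 infant runs to day 21.
2. Schedule 29-week infants in both arms toward the end of the window where feasible. This gains up to 6 days.
3. Reconcile the 3 and 7 weeks in 3.2.6 with the start day in the abstract and the window in 3.2, and state whether the ±2 days applies to the tracer window.
4. Record the interval from decision to tracer (from the matching postnatal day in controls). In 5.2.2, pre-specify a supportive analysis by that interval, keeping all randomised infants in the main comparison. The interval is largely set by gestational age at birth, so this analysis cannot separate the two.

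The cost is a few sentences, with no added procedures or patients. The downside is less scheduling flexibility and a slightly later postmenstrual age at measurement for 29-week infants, equal in both arms.

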3.2.1 Screening

All patients admitted to Riley Hospital at IU Health's NICUs (Simon Family Tower, Methodist, IU North), and Eskenazi Health NICU, will be evaluated for eligibility. Outborn infants will be included if admitted within the first week of life.

3.2.2 Consent Procedure

Eligible infant's guardians will be approached for consent by study personnel after the infant's first week of life.

3.2.3 Randomization Procedure

An infant must meet all inclusion criteria and no exclusion criteria at the time of randomization. After meeting eligibility and obtaining consent, randomization will be carried out in REDCap to management arms 1:1, using a permutated block scheme stratified by gestational age at birth: $25 \, \text{O}/7 - 27 \, \text{O}/7$ and $28 \, \text{O}/7 - 29 \, \text{O}/7$ weeks.

3.2.4 Study Intervention

Infants randomized to the study algorithm will have their urine [Na] measured at 2 weeks of age and every 2 weeks thereafter until 36 weeks corrected age. They will receive additional sodium supplementation after the second week of life if their urine [Na] is below the level in the diagram on the following page:

Postnatal	2	3	4	5	6	7	8	9	10	11	12	13	14
age (weeks)													
GA (birth)													
25 wk	<50		<40		<40		<40		<40		<30		<30
26 - 29 6/7 wk	<40		<40		<40		<40		<30		<30		

- i. Values in table represent urine [Na], expressed as mEq/L, obtained every other week
- ii. If urine [Na] is below threshold value, initiate supplementation at 4 mEq/kg/d above current Na intake. Adjust supplementation weekly to account for weight gain
- iii. Increase supplementation by 2 mEq/kg/d at subsequent biweekly points if <urine [Na] goal. Urine [Na] should not be obtained within 48 hr of use of diuretic agent
- iv. Provide supplementation if serum [Na] ≤132 mEq/L regardless of urine [Na] unless there is evidence of acute fluid overload (significant increase in weight). Hyponatremia in presence of high urine [Na] likely represents a condition of severe urinary sodium loss leading to hyponatremia
- v. Continue supplementation unless serum [Na] >144 mEq/L

If serum [Na] 145 – 146 mEq/L; reduce sodium supplement by ½ and consider measuring serum [Na] on subsequent day

If serum [Na] ≥ 147 mEq/L; discontinue sodium supplementation

vi. Continuation of supplementation after 38 weeks postmenstrual age will be at the discretion of the clinical care team

Routes of sodium administration:

We will allow flexibility in how supplemental sodium is delivered since this is not standardized in usual care practices.

For infants receiving ≤80 ml/kg/d of enteral feedings: The designated amount of sodium supplementation will be added to parenteral fluids to be infused over 24 hours. Sodium may be provided as sodium chloride acetate/citrate/bicarbonate or any mixture thereof.

For infants receiving >80 ml/kg/d of enteral feedings: The designated amount of sodium will be added to the feedings (sole route of supplementation) or provided by a combination of enteral and parenteral route. When provided enterally, sodium will be administered in equally divided quantities with every other feeding, (i.e., 4 feedings each day for infants fed every 3 hours, 3 feedings each day for infants fed every 4 hours). Enteral supplemental sodium may be administered in the form (sodium chloride, sodium acetate, sodium citrate, sodium bicarbonate, or any mixture) chosen by the care team.

3.2.5 Data collection:

Growth and nutrition data, including fluid, caloric, protein, carbohydrate and lipid intakes and weight, will be abstracted from the infants' medical records and entered on to study data collection instruments. Standardized data collection forms will be used for collection all clinical outcome data and entered into a REDCap data base as described below. Other variables will be recorded on data forms created for this trial. The potential confounding variables include but are not limited to:

- Maternal demographic variables: maternal age, maternal education level, maternal race/ethnicity, maternal health issues, presence of chorioamnionitis, preeclampsia, reason for preterm delivery
- Labor and delivery: rupture of membranes, steroid exposure, antibiotics, mode of delivery
- Infant health demographic variables: gestational age at birth, birthweight, length, sex, small for gestational age status, parity, Apgar scores, delivery room resuscitation, initial respiratory support, blood pressure, body temperature, pH, PaO2, FiO2.
- Infant neurologic and medical morbidity: death, presence and severity of intracranial hemorrhage, presence of periventricular leukomalacia, seizures, patent ductus arteriosus, early and late onset sepsis, bronchopulmonary dysplasia, retinopathy of prematurity (stage ≥3 or requiring treatment), age at final tracheal extubation, length of hospital stay, duration of need for supplemental oxygen and diagnosis of hypertension as defined as need for scheduled antihypertensive agents.
- Nutritional intake data: Parenteral intake of fluid, protein, lipid, calories and sodium will be recorded each Monday, Wednesday and Friday from day of life until 38 weeks postmenstrual age or hospital discharge. Enteral intake of milk/formula volume, sodium and calories will similarly be recorded each Monday, Wednesday and Friday. Sodium content of breast milk will be estimated at 0.8 mEq/100 ml. Milk fortified to 24 and 27 kcal/oz with human milk fortifier (HMF) will be estimated to have sodium content of 1.4 and 1.8 mEq/100 ml, respectively. Sodium content of formula will be as described by the manufacturer.
- Anthropomorphic measurements: Measurements will be obtained weekly until discharge/transfer or until 44 weeks corrected age (whichever occurs first). Weights will be

extracted from the medical record. Research staff will obtain the length (using a length board) and OFC.

3.2.6 Measurement of Total Body Water and Energy Expenditure

Total body water (TBW) and energy expenditure (EE) will be determined at 32 weeks postmenstrual age. This approach will provide TBW and EE measurements over a range of postnatal ages following initial supplementation (*i.e.* 3 weeks for infants born at 29 weeks gestation, 7 weeks for infants born at 25 weeks gestation) allowing an understanding of changes in TBW and EE over time after initiating supplemental Na. EE and TBW will be measured using the doubly labeled water (DLW, $^2H_2^{18}O$) method which has been validated in preterm and term infants[53-56]. The method uses non-radioactive isotopes, is non-invasive and does not require blood sampling. The method is based on the principle that labeled hydrogen (2H) is eliminated as water, disappearance of the oxygen isotope (^{18}O) is eliminated as water and as expired carbon dioxide. By measuring the difference in the elimination rates, carbon dioxide production can be calculated according to the following equations:

$$rCO_2 = 0.445N \times [(1.01 \times ko) - (1.04 \times kh)]$$

where rCO_2 is carbon dioxide production rate, N is the mean of the initial and final TBW volume calculated as described below, ko and kh are the fractional elimination rates for ^{18}O and $^{2}H_2$, respectively.

Metabolic rate is estimated from rCO₂ using Weir's equation based on the food quotient (FQ) of dietary intake:

$$EE(kcal/d) = 1.44 \times [[3.941 \times rCO_2(ml/min)/FQ] + 1.11 \times rCO_2(ml/min)]$$
 Food quotient (FQ), used as an estimate of respiratory quotient is calculated as:
$$FQ = (P \times 0.81) + (F \times 0.71) + (C \times 1.00)$$

Where P, F and C represent the energy contributed by protein (P), fat (F) and carbohydrate (C) expressed as a fraction of the total metabolizable energy of the diet[57]. Published values for human milk and infant formula will be used as applicable and modified as necessary for any dietary supplementation (i.e. human milk fortifier) provided.

TBW (g) is estimated from the dilution of ²H using the following equation as previously described by us and others[58-60].

TBW = [Dose x W x
$$(\delta_d - \delta_w)$$
]/(D x I₀ x 1.041)

where Dose is the weight (g) of the DLW administered, W is the weight (g) of water used to prepare the dose dilution, δ_d is the $\delta^2 H$ value (°/oo) of the dose dilution, δ_w is the $\delta^2 H$ value (°/oo) of the water used in making the dose dilution, D is the weight (g) of the DLW used to prepare the dose dilution, I_0 is the zero-time intercept (°/oo) of the $^2 H$ enrichment over time, and 1.041 is the correction for deuterium distributed into non-aqueous tissues. Urine $^2 H_2 O$ enrichment at time 0 is extrapolated by linear regression analysis after plotting the logarithm of $^2 H_2 O$ enrichment in urine versus time.

A typical study protocol using the DLW method starts with a baseline urine collection before the dose of DLW to determine baseline values for ²H and ¹⁸O. An accurately weighed dose of DLW (1.5g/kg body weight, ²H₂O (99.9 atom %) and H₂¹⁸O (10.0 atom %) (both from Children's Nutrition Research Center at Baylor College of Medicine) is administered through a nasogastric feeding tube. DLW sterility is ensured using microfiltration into single use sterilized serum vials that are then covered with parafilm. The dose (approximately 1.5 ml/kg) is flushed through the tube with 2 ml of sterile water. The syringes containing the isotopes are weighed to the nearest 0.1 mg before and after the dose is given. Urine samples are then collected between 6-24 h after dosing and, and again 2 and 5 days after dosing. Timing of urine collection is carefully recorded. These urine samples will be analyzed for ²H and ¹⁸O enrichment by isotope ratio mass spectrometry, which will allow for calculation of TBW and EE as described above[61,62].

Urine will be collected, labelled appropriately, including time after DLW administration, and frozen at -20°C until shipped for analysis. Samples will be shipped from IU to the USDA/ARS Children Nutrition Research Center at Baylor College of Medicine and immediately transferred to the Central DLW Laboratory, directed by [name], a collaborator on the project. Upon arrival, samples will be logged and again frozen at -80°C until isotope analysis is performed by gasisotope-ratio mass spectrometry as performed in [name] laboratory as previously described[63].

